Statistical analysis plan (SAP)

Section 1. Administrative information

1a. Title, registration, versions and revisions

Full study title: Effectiveness of Written Dietary Advice on Lipoproteins - a Pragmatic Randomized Controlled Trial

Acronym: MYDICLIN

1b. Clinicaltrials.gov identifier: NCT03528252

2. SAP version: 1.4, 2019-04-18

3. Protocol version: Research plan version 18-09-20

4. SAP revisions: No major revisions.

5. Roles and responsibility

Author: [name]^{1,2}

Principle Investigator: [name]^{1,2}

Affiliations:

- 1. Unit for Clinical Nutrition and Metabolism, Deptartment of Public Health and Caring Sciences, Uppsala university.
- 2. Center for Clinical research Dalarna

6. Signatures:

I the undersigned, certify that I have read this SAP and approve it as adequate in scope of the main analyses of MYDICLIN.

6. Author and principle investigator

Name: [name]

Date: 2019 - 04 - 18

Section 2. Introduction

7. Background and rationale

Dietary factors are of major importance for public health, but effective means are lacking, to improve dietary habits of patients in primary care. This pragmatic trial aims to investigate whether detailed written dietary advice may be an effective way of improving blood lipoproteins in a Swedish primary care setting.

8. Objectives

The main purpose is to investigate whether written dietary advice with individual written feedback can affect blood lipoproteins in the short-term (3 weeks) and medium-term (6 months).

Specific aims

- What effect does written dietary advice have on LDL cholesterol (primary outcome) and other lipoproteins and risk factors (secondary outcomes) after 3 weeks and 6 months, compared with a control group?
- What proportion of individuals achieve a ≥10% reduction in LDL cholesterol from baseline, after and 6 months?
- In the group of responders (≥10% reduction in LDL cholesterol from baseline), what is the effect after 3 weeks and 6 months?
- Is double sampling of LDL cholesterol required in clinical practice, i.e., how many would be misclassified as responders/non-responders if only one sample was taken at 3 weeks and 6 months?
- How does the intervention's cost compare with estimated future health care savings, as estimated per mean LDL cholesterol reduction, and per individual reaching ≥10% reduction in LDL cholesterol at 6 months?
- Which food choices are associated with reductions in LDL cholesterol in practice?

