P<0.05 will be considered as statistically significant for primary outcomes. For secondary outcomes, significance testing is not as essential as they are mainly hypothesis generating.

17. Adjustment for multiple analyses

The primary outcome is change in LDL cholesterol at 3 weeks and 6 months. The power calculations have been performed for between-group differences at 6 months and this analysis is considered the primary outcome of the study. Thus, no adjustment for multiple analyses will be performed.

18. Confidence intervals

N/A.

Adherence and protocol deviations

19a. Definition of adherence to the intervention

Being randomized and completing the trial (day 183) is considered as sufficient for adherence. For the visit at 3 weeks, no more than 2 days' deviation from protocol will be allowed. For the visit at 183 days, no more than 2 weeks' deviation will be allowed.

19b. Description how adherence will be presented

No specific information on adherence will be presented, besides no. of participants randomized and completing the trial at 3 weeks and 6 months, and no. excluded before and after randomization, with reasons.

19c. Definition of protocol deviations

Deviations from time schedule. Failing to be overnight fasting at time points 2, 4 or 6.

19d. Description of which deviations will be summarized

In cases in which blood samples are taken on the wrong day, the no. of deviations and number of days' deviation from protocol will be reported for each time point. Also, the number indivduals who failed to be completely fasting at time points 2, 4 and 6 will be given.

20. Analysis populations

Study populations will be analyzed according to intention-to-treat principles.

Section 5. Trial Population

21. Screening data

N/A (not collected).

22. Eligibility criteria

Inclusion criteria: patients listed at the health care centre, wish to improve blood lipoproteins, ages 18-99 years.

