For LDL Cholesterol baseline (BL) values will be calculated as the arithmetic mean of values at day -3 and day 0 [(d-3+d0)/2], similarly, values at 3 weeks will be calculated as the arithmetic mean of values at days 18 and 21 [(d18+d21)/2] and values at 6 months will be calculated as the arithmetic mean of values at days 180 and 183 [(d180+d183)/2].

For all continuous variables, absolute change from baseline (Δ) will be calculated at 3 weeks and 6 months as [Δ = 3w - BL and 6m - BL]. Relative change from baseline (% Δ) will be calculated as [% Δ = (3w - BL)/BL and (6m - BL)/BL].

As a sensitivity analysis, variables in the GLM with non-normal distribution will be log transformed (otherwise, no transformations will be performed).

Analysis methods

27a. Analysis methods and presentation of results

Between-group differences for change from baseline (Δ) in continuous variables will be significance tested using a general linear model (GLM). For LDL cholesterol, the results will be presented as a figure with boxplots displaying values at BL, 3 weeks and 6 months for each group. Also, a boxplot of Δ -values at 6 months will be presented for each group. The results will be given in a table format, displayed as mean±SD change from baseline, and P-values for difference between groups.

Difference in mean change from baseline in LDL cholesterol (and triglycerides for control group) between 21 and 18 days and 183 vs. 180 days will be analyzed with t-tests.

Secondary outcome no. 4 (success rate) i.e. the no. and proportion of individuals that achieve a $\leq 0\%$, >0 to <10% or $\geq 10\%$ reduction in LDL cholesterol from baseline will be analyzed by logistic regression, adjusted for age, sex and baseline BMI. No. of individuals that develop impaired fasting glucose will be compared between groups with Fisher's exact test (unadjusted).

Secondary outcome no. 8 (effective food choices) will be analyzed and presented as linear regressions between number of X:s for food choices 1-13 (and the total number of X:s) and change in LDL cholesterol (or Triglycerides within Control group) at 3 weeks and 6 months.

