Secondary outcome no. 9 (stated reasons) will be categorized into main groups of reasons according to given responses (one, two or three compared to none stated), no. in each group and mean changes in LDL cholesterol (or triglycerides) as well as total number of X:s (and proportions of total number of possible X:s for both groups combined) will be given as means+SD in table format. For within-group effects on mean LDL cholesterol at 3 weeks and 6 months, paired t-tests will be performed in intervention group (the same for triglycerides in control group). For proportion of total X:s, differences compared with reference group (none stated) will be analyzed by Mann Whitney U-test.

27b. Adjustment for covariates

Comparisons of means in the GLM will be adjusted for the baseline value of the variable, baseline BMI, age and sex.

For success rate, the logistic regression will be adjusted for the covariates baseline LDL cholesterol, baseline BMI, age and sex.

Linear regressions for food choices and lipoproteins will be unadjusted.

27c. Tests for assumptions

Normality of data will be determined by visual inspection of histograms and QQ-plots. No other tests for assumptions will performed. The underlying assumptions of the GLM will be tested by examining residuals.

27d. Alternative methods if distributional assumptions do not hold

As a sensitivity analysis, variables in the GLM with non-normal distribution will be log transformed (otherwise, no transformations will be performed).

27e. Planned sensitivity analyses

For all comparisons of means of continuous outcomes, unadjusted Mann Whitney U-tests will be performed as sensitivity analyses.

27f. Planned subgroup analyses

In order to investigate whether different baseline characteristics are associated with success rate (outcome no. 4), responders (≥10% decrease in LDL cholesterol or Triglycerides) and non-responders at 3 weeks will be analyzed with descriptive statistics regarding age, sex, baseline cholesterol, no. with diabetes and impaired fasting glucose, systolic and diastolic blood pressure, no. of X:s (total and for each food choice), and reasons stated (according to categories), separately for both study arms. Comparisons between responders and non-responders will be analyzed by t-tests and Fisher's exact test. Similar analyses will be performed for successful individuals at 6 months (≥10% decrease in LDL cholesterol or Triglycerides).

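### SAP 27b fixes the food-choice regressions as unadjusted, so a slope labelled as an effective food choice may only reflect general diligence; adjusted slopes should be reported beside them

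*SAP*

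**What the plan says.** The aim in SAP section 8 is worded as association: "Which food choices are associated with reductions in LDL cholesterol in practice". The analysis in 27a is labelled more strongly: "Secondary outcome no. 8 (effective food choices) will be analyzed and presented as linear regressions between number of X:s for food choices 1-13". The total tick count is a further regressor. The outcome is change in LDL cholesterol (triglycerides within the control group) at 3 weeks and 6 months. Section 27b then states "Linear regressions for food choices and lipoproteins will be unadjusted". Because the total is the sum of the 13 foods, it cannot share a model with all of them, so this means one regressor per model.

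The same section treats the between-group analyses differently: "Comparisons of means in the GLM will be adjusted for the baseline value of the variable, baseline BMI, age and sex", and for success rate "the logistic regression will be adjusted for the covariates baseline LDL cholesterol, baseline BMI, age and sex". The sensitivity analyses in 27e cover comparisons of means, so no adjusted version of the food slopes is planned. SAP 16 sets the status of such results: "For secondary outcomes, significance testing is not as essential as they are mainly hypothesis generating".

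**The concern.** Only the advice sheet is randomized. Each food's exposure is a count of days that the participant chose to act and marked in the table (Protocol, Methods). Someone who follows the sheet diligently is likely to have high counts on several items. A model with one food credits that food with whatever the others, or diligence in general, did to LDL. The output cannot then tell an effective food from a diligent participant, yet the SAP's label invites the first reading. A wrong list of effective foods could shape the next version of the advice. Baseline LDL is a second possible route, because change from baseline usually depends on the baseline value.

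**Working it through.** The documents give no figure for these regressions, so there is none to reproduce.

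**Inputs from the SAP.** 113 participants allocated 1:1 give 113/2, about 56 per arm (sections 9 and 11). There are 13 foods plus the total, and two time points (27a).

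**Assumptions.** Common correlation ρ between food counts of 0, 0.3 or 0.5. Either one active food, or general diligence alone, correlates 0.35 in size with change in LDL. Nominal P<0.05 is used as a yardstick.

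**Step 1: inert food, unadjusted.** If its marginal correlation with LDL change is r, the noncentrality is λ = r√n/√(1−r²). The flag rate is the chance that a noncentral t on 54 df exceeds 2.005 in size.

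- One active food: r = 0.35ρ.
- Diligence only: a count that shares correlation ρ through one common factor correlates √ρ with that factor, so r = 0.35√ρ.

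| Case | ρ | r | λ | Flag rate, formula | Flag rate, simulation |
|---|---|---|---|---|---|
| Either | 0 | 0 | 0 | 5% | about 5% |
| One active food | 0.3 | 0.105 | 0.79 | 12% | about 12% |
| One active food | 0.5 | 0.175 | 1.33 | 26% | 22–26% |
| Diligence only | 0.3 | 0.192 | 1.46 | 30% | 28–33% |
| Diligence only | 0.5 | 0.247 | 1.91 | 47% | 45–46% |

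With three active foods that together explain 10% of the variance of change, simulation gives 16% (ρ=0.3) and 31% (ρ=0.5). At 20% explained it gives 28% and 55%. If no food is active and neither diligence nor baseline matters, the rate is 5% even when counts correlate.

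**Step 2: inert food, adjusted for the total of the other foods.** Under equal correlations, the expected count of the active food given the inert food and the other-food total T is T/12. The inert food's slope is therefore exactly zero, and simulation gives about 5%. When only diligence matters, T is a good but imperfect proxy, and simulation gives 5–6%.

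**Step 3: price in power.** A food's correlation with the total of the other 12 is 12ρ/√(12+132ρ), which is 0.501 at ρ=0.3 and 0.679 at ρ=0.5. The variance left is 1−0.501² = 0.749 and 1−0.679² = 0.538. For the active food λ falls from 2.80 to 2.80×√0.749 = 2.42, or to 2.80×√0.538 = 2.05. Power falls from 78% to 66% or 52% by formula. Simulation gives 77% to 63% and 76% to 51%.

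**Step 4: baseline LDL.** It shifts a food slope only if it correlates with that food's count. Suppose that correlation is 0.3, the slope of change on baseline is −0.15, baseline SD is 0.9 and SD of change is 0.40. Baseline then correlates −0.15×0.9/0.40 = −0.34 with change, and simulation flags inert foods in 11–12% of tests. At zero correlation there is no bias. Adjustment then only removes residual variance: with a baseline–change correlation of −0.25 to −0.31 (assumed), 0.25² to 0.31², or 6–10%.

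**Step 5: number of tests.** Under 27a there are 14 regressors × 2 time points = 28 slopes per arm, so 28×0.05 = 1.4 chance hits. If every continuous outcome in 26a is regressed, there are 14×14×2 = 392 slopes and 19.6 chance hits.

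**The case against.** The aim asks only which foods go with LDL reduction in practice, and a marginal slope answers that. Secondary outcomes are declared mainly hypothesis generating. Section 26a also lists each food's proportion of total ticks, which might partly separate food mix from diligence. Adjustment costs power in a small arm.

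Much of this stands. It is the reason to keep the unadjusted slopes and add to them. It does not remove the problem. Exploratory status relaxes the threshold but leaves confounding in place, the label in 27a goes beyond association, and 27a does not carry the proportion into the regressions. The power loss is severe if all 13 foods enter together: in the three-food case with 10% explained and ρ=0.5, power per active food drops from 50% to 11%. It is moderate with one composite of the other foods.

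A reader might also infer more than the documents support:

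- *Inert foods will be reported as effective.* This needs correlated counts plus a real food or diligence effect, or counts correlated with baseline LDL. The documents report none of these and exclude none.
- *Every slope absorbs baseline LDL.* This holds only under the condition in step 4.
- *Every other LDL analysis adjusts for baseline.* The paired t-tests, Mann-Whitney tests and responder comparisons do not. For the success-rate model, 27a omits baseline LDL while 27b includes it.
- *392 tests are planned.* That is the widest reading of 26a; 27a specifies 28 per arm.

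**Conclusion.** The concern holds in conditional form. The plan fixes single-food, unadjusted slopes for self-selected behaviours, gives them a causal-sounding label, and has no adjusted counterpart. Under assumed between-food correlations of 0.3 to 0.5 and an effect of one food or of diligence (correlation 0.35), an inert food is nominally significant in roughly 12 to 45% of tests, against about 5 to 6% with adjustment. With uncorrelated counts the rate stays at 5%. The correlations and effect sizes are assumptions; only the arm size and the 13 foods come from the SAP. This is an inexpensive improvement to a secondary, exploratory outcome, and the primary result does not depend on it.

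**What to change.** Replace the sentence in 27b so that each food slope is estimated twice: unadjusted, and adjusted for the baseline value of the outcome, baseline BMI, age, sex and the total ticks for the other food choices. Report the two side by side with 95% confidence intervals, and state the number of tests (28 per arm under 27a; up to about 392 if every outcome in 26a is regressed). A table of correlations between the food counts would show whether the assumed range applies. Call a food effective only if the adjusted slope supports it; otherwise describe the result as an exploratory association.

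The cost is a change of SAP wording and a rerun of the same regressions on data already collected. The adjusted model has less power for a single active food, as in step 3, which is why it should not replace the unadjusted one. Adjustment also leaves multiplicity in place: if independent, 13 tests at 5% still give 1−0.95¹³ = 49% chance of at least one false hit, and 28 tests give 1−0.95²⁸ = 76%.

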- What are the reasons given for wanting to reduce LDL cholesterol? Is there any association between reasons given and effect on LDL cholesterol?

Section 3. Study Methods

9. Trial design

The study design is a pragmatic randomized controlled dietary trial, with two parallel arms. The allocation ratio is 1:1. Both groups will receive dietary advice in sealed numbered envelopes. The intervention group will receive advice for reducing LDL cholesterol, whereas the control group will receive similar advice, but instead proven effective for reducing fasting triglycerides. The participants will not be aware of which group is considered as active intervention. Participants were recruited and randomized May to October 2018 and data collection is finished April 18th 2019.

10. Randomization

The allocation sequence is created by an external agent and performed in blocks (size unknown to investigators). The allocation sequence will be concealed until data collection has been completed.

11. Sample size

A primary power calculation was performed based on previous randomized intervention studies of dietary fat quality and effects on lipoproteins. At least n=222 participants were required (for alpha = 0.05 and beta = 0.10) to detect an effect in LDL cholesterol of 0.175 mmol/L (~5%), which would slightly exceed that in most previous studies, parallel within-individual day-to-day variation (at double sampling), and have some clinical significance. This calculation took into account a 20% loss to follow-up in the intervention group and a contamination effect of 5% in the control group.

In September 2018, during the end of recruitment process, another power calculation was performed in order to examine the power given the current recruitment status (n=104). For alpha = 0.05 and beta = 0.20, the minimum number of participants required was n=106 (n=94 without 5% contamination). Thus, the recruitment was considered as finished at Oct 16th, when n=113 participants were included (as the number of volunteer participants had faded, and power was considered sufficient, if not optimal).

12. Framework

The study is a dietary intervention with clinical and experimental outcomes.

13. Stopping interim analyses

N/A.

14. Timing of final analysis

All analyses will be performed once data collection is finished, April 18th 2019.

15. Timing of outcomes assessment

N/A.

Section 4. Statistical principles

Confidence intervals and P values

16. Level of statistical significance

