Further, subgroup analyses will be performed in young (<65 years) vs elderly (65+) individuals, in order to establish whether results are homogenous in these subgroups, for guidance of future studies.

28. Missing data

When data are missing due to loss to follow-up, baseline values will be imputed. If only one time point 3 or 5 is missing (LDL cholesterol at d18 or d180), the mean LDL

cholesterol value will instead be assumed to be the exact value at time point 4 or 6 (d21 or d183).

29. Additional analyses

For possible future analyses (see 26a. secondary outcomes), analyses will be performed with similar methods as other continuous/categorical variables.

30. Harms

Reported adverse effects (if any) will be described in text or table format, depending on the outcome. No serious adverse effects are expected and severity will not be summarized separately.

31. Statistical software

IBM SPSS Statistics 25 will be used for all analyses.

32. References

Data management plan, standard operating procedures, dietary advice, food records and study letters will be stored separately and not provided at trial registry during the study. No statistical master file has yet been created and public access will not be granted.

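### Does the log-transform sensitivity analysis require the logarithm of change scores that are negative or zero?

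*SAP*

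**What the plan says.** SAP 26c defines the change score: "For all continuous variables, absolute change from baseline (Δ) will be calculated at 3 weeks and 6 months as" follow-up minus baseline, so a fall is negative. SAP 27a makes this the tested outcome: "Between-group differences for change from baseline (Δ) in continuous variables will be significance tested using a general linear model (GLM". SAP 27b lists the covariates: "Comparisons of means in the GLM will be adjusted for the baseline value of the variable, baseline BMI, age and sex".

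For outcomes that are not normal, 26c and 27d carry the same sentence: "As a sensitivity analysis, variables in the GLM with non-normal distribution will be log transformed (otherwise, no transformations will be performed". It gives no log-ratio model, log follow-up model or offset constant. SAP 27c bases the normality judgement on histograms and QQ-plots and does not say whether measured values or Δ are plotted. The protocol's section on statistical analyses mentions no log transformation.

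Two other provisions bear on the point. Section 28 states: "When data are missing due to loss to follow-up, baseline values will be imputed". Section 27e adds a second sensitivity analysis: "For all comparisons of means of continuous outcomes, unadjusted Mann Whitney U-tests will be performed as sensitivity analyses".

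**The concern.** Read literally, the rule logs whatever is in the GLM, and 27a puts Δ there. A logarithm needs a positive number. Every participant whose value fell has a negative Δ. Every participant lost to follow-up has a Δ of exactly zero under section 28. A model for log(Δ) would keep only participants whose value rose, in a trial meant to lower lipids. That is selection on the outcome, and it would contradict the intention-to-treat statement in section 20.

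The log model is also the only covariate-adjusted fallback for a non-normal outcome, because the Mann-Whitney tests are unadjusted. Fasting triglycerides, the target of the control advice, would be the likeliest outcome to need it.

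**Working it through.** The plan states no figure on this point, so there is none to reproduce. The check has four steps.

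**1. What happens if Δ is logged.** Inputs from the SAP: 113 participants, a planned effect of 0.175 mmol/L and 20% loss in the intervention group (section 11), and 1:1 allocation (section 9). The documents give no SD for change in LDL cholesterol, so I assume 0.3 to 0.6 mmol/L, a normal Δ and no mean change in controls.

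- Undefined share, intervention = 0.20 + 0.80 × Φ(0.175/SD)
- Undefined share, control = Φ(0) = 0.50

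| SD (mmol/L) | Φ(0.175/SD) | Intervention | Control | Overall | Of 113 |
|---|---|---|---|---|---|
| 0.3 | 0.720 | 0.20 + 0.80 × 0.720 = 0.776 | 0.50 | 0.638 | 72.1 |
| 0.6 | 0.615 | 0.20 + 0.80 × 0.615 = 0.692 | 0.50 | 0.596 | 67.3 |

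These figures only give scale. They assume a normal Δ, which is the case least likely to trigger a log step reserved for non-normal data.

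**2. What happens if measured values are logged.** Concentrations, blood pressure, weight and waist are all positive, so every logarithm exists. A participant with imputed baseline contributes log(BL/BL) = 0 and stays in the model. Undefined: 0 of 113.

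It also makes no difference whether the analyst models the log ratio or the log follow-up value, provided log(BL) is a covariate:

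- log(FU) − log(BL) = a + b·arm + c·log(BL) + other covariates
- is the same model as log(FU) = a + b·arm + (c + 1)·log(BL) + other covariates

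The arm effect b is identical, so this reading leads to one answer.

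**3. Which reading the SAP's wording supports.**

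- 25b: non-normal variables are summarised by median and IQR. These are measured baseline characteristics, and the phrase is the closest parallel to the disputed sentence.
- 26c: Δ is calculated for continuous variables, so the variable is what Δ is calculated from.
- 27a: Δ is a change in continuous variables, with the same distinction.
- 27b: adjustment is for the variable's baseline value. A change score has no baseline value.

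In all four places the variable is the measured quantity and Δ is derived from it. Read the same way, "variables in the GLM with non-normal distribution will be log transformed" means logging the measured values.

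**4. What the sentence can affect.** It is labelled a sensitivity analysis. The primary comparison, LDL change at 6 months, comes from the untransformed GLM. The Mann-Whitney tests depend on ranks and need no logarithm. Triglycerides are a secondary outcome, and section 16 treats secondary outcomes as mainly exploratory.

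**The case for a change.** The strongest case for amending the SAP is that a pre-specified analysis should name its outcome. In 26c the sentence comes directly after the definitions of absolute and relative change, and 27a names Δ as what the GLM tests, so a literal reader could land on Δ. A third reading, logging only a skewed covariate such as BMI, also fits the words. Logging also turns the effect into a ratio, which the SAP does not mention.

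Part of this stands. The logged quantity is not named, and the change of scale is left unsaid. Neither leads to a wrong result. Logging Δ fails visibly: the software returns missing values for well over half the sample on the figures above, so nobody could report it unawares. A ratio of geometric means is what any log-scale comparison gives, and the analyst would label it so. Logging a covariate alone drops nobody and leaves the outcome in its original units.

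A power comparison between a log(Δ) model and a log follow-up model would not strengthen the case. It would rest on the less plausible reading and on a spread, a correlation and an effect ratio found in neither document.

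**Conclusion.** The concern is right that log(Δ) cannot be computed for falls or for baseline-imputed zeros, and right that 26c and 27d do not name the logged quantity. It does not call for a change. The SAP's usage in 25b, 26c, 27a and 27b points to the measured values, and on that reading 0 of 113 participants are lost and the arm effect is uniquely determined. The loss of roughly 67 to 72 participants arises only on the other reading, under an assumed SD of 0.3 to 0.6 mmol/L, and would be obvious at the first run. The primary GLM, the Mann-Whitney tests and every primary conclusion are untouched. The sentence's closing restriction, which bars other transformations, is also useful and would be lost if the sentence were simply replaced. This is missing detail in a sensitivity analysis that analysts fill sensibly. The conclusion rests on the SAP's consistent use of *variable* and on measured values being positive.
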